Enhancing Panic and Smoking Reduction Treatment with D-Cycloserine

NCT01944423

Last updated: 6/7/2017

Data Analysis.

Overview. First, we will assess the equivalence of the treatment groups on key baseline variables (demographics, smoking characteristics, psychological variables); variables on which the groups differ will be used as a covariate in final analyses. We will then examine missing data patterns, dropout rates (see below), and distributional properties of measures and use transformations to improve distributions when necessary.

Following recommendations of the Society for Research on Nicotine and Tobacco (Hall et al., 2001), the effects of treatment on PPA will be examined using Generalized Linear Mixed Models (GLMM), employing the logistic linking function. In our GLMM analyses, the repeated measures will be nested within individuals, which will be nested within their treatment cohort, thereby appropriately accounting for correlated scores within the small cohorts. Our GLMM analysis will model outcome as a curvilinear (quadratic) or exponential function of time (based on AIC and BIC) since PPA is expected to decrease rapidly at first and then level off over time. Using this model, one can test differences between treatment groups by including treatment condition as an “individual level” predictor of rate of decrease in PPA over time. We can also examine treatment group differences in PPA at any assessment point. Multi-level models (MLMs) similar to the GLMM models will be used to test treatment differences in continuous outcomes (the psychological variables: withdrawal symptoms, negative affect, panic severity, distress intolerance, and anxiety sensitivity). All models will include relevant control variables (e.g., gender, education, nicotine dependence, etc.). We will also run a Cox proportional hazards survival analysis predicting risk of lapsing or relapsing to smoking and compare the two conditions on these outcomes.

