Tests of specific aims. Aim 1a: Treatment differences in slopes will indicate different rates of decrease in PPA. To determine whether there are treatment differences in PPA at any particular time point (e.g., week 24), we will center the “Time” variable in the GLMM model at that time point (Singer & Willett, 2003). **Aim 1b:** Cox proportional hazard models will be used to test for differences between treatments in relative risk of lapse and relapse, and in time to first lapse and to relapse. **Aim 2a:** The same analyses in Aim 1a will be used in MLMs to test for treatment differences in the psychological outcomes (withdrawal symptoms, negative affect, panic severity, distress intolerance, anxiety sensitivity). **Aim 3a:** The “a” paths in our mediation model (see Figure 1 in Specific Aims) will be calculated as in Aim 2a. Because we expect the “a” paths to be moderated, separate analyses will be conducted to calculate the “a” paths for each treatment condition (Tein, Sandler, MacKinnon, & Wolchik, 2004). The “c” path will be calculated as in Aim 1a. **Aim 3b:** The “b” paths in our mediation model will be the regression coefficients for the mediators when all the mediators are simultaneously added to the GLMM equation predicting PPA used in Aim 1a. **Aim 3c.** Tests of the mediated pathways will be conducted separately for each treatment condition (due to moderated mediation [Tein et al., 2004]). Significance of mediated pathways will be determined using Bayesian bootstrap mediation analysis (Yuan & MacKinnon, 2009).

Missing Data. Following Hall et al. (2001) and Enders (2011), we will use pattern mixture modeling to assess the effect of missing data. We will rerun our analyses coding for various missing data patterns (no missing data, sporadic missing, dropouts, etc.) to determine both if missingness impacts our findings and how the differences between PSRT+DCS and PSRT+PBO depend on the missing data pattern.

Power Analysis. Because we will have a sample size of 80, this application is not powered to detect small differences between treatment conditions. However, consistent with the aims of a Stage IB study, our primary goal is determining 1) the feasibility of the new intervention and 2) whether a Stage II study is warranted. Below we estimate (for the lowest powered analyses) the effect sizes (ESs) that we will be able to detect as statistically significant with 80% power.

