Aim 1a: GLMM model comparing PPA in the PSRT+DCS condition vs. the PSRT+PBO condition. We performed a Monte Carlo study to calculate the minimum PSRT+DCS PPA rate detectable by our analysis. Our assumptions were: an average of 5 assessments per participant (71% of the post quit date assessments) ([name] et al., 2008) and a 27% PPA in PSRT+PBO at the last follow-up (Piper et al., 2010). We examined numerous PSRT+DCS PPA rates to determine the lowest rate detectable by our analysis, performing 1000 simulations for each PPA rate. The results indicated that we would have .80 power to detect a significant treatment effect if the PPA rate in PSRT+DCS at the follow-up was 43% or greater. This difference – i.e., 43% vs. 27% - is equivalent to a Cohen's ω effect size (the effect size measure for proportions) of .17, between a small (.10) and medium (.30) ω effect size (Cohen, 1988). Thus, we have sufficient power to detect a smaller than medium effect.

Aim 3: Moderated Mediation of changes in PPA. The first step in our moderated mediation power analysis was to determine the power to detect moderation of the “a” path (see Figure 1. Using the MLM power analysis program PinT 2.12 (Snijders & Bosker, 1993) to calculate our power to detect moderation of path “a”, we found that we had over .95 power to detect a medium effect size ($d = .50$) for moderation of the “a” path. Next we calculated the power to detect longitudinal mediation for each treatment group, over time. For this analysis, path “a” was the slope of change in the mediator over time, and path “b” was the relation between the mediator and the outcome over time. We performed a Monte Carlo study to calculate the power for a bootstrap mediation analysis. We assumed that the effect sizes for the “a” paths (the change in the mediators over time) would be large ($d > .80$; see 3C.2a), the effect size for the “b” paths would be medium, and the PPA rates were assumed to be those found in Aim 1a (27% for PSRT+PBO and 43% for PSRT+DCS). The Monte Carlo study consisted of 400 samples, for each of which we performed a bootstrap mediation analysis each consisting of 1000 resamples. Results indicated that we would have at least .81 power to detect a mediated effect.

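### Aim 3b takes path b from an undivided mediator coefficient, so stable differences between smokers can pass for mediation

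*SAP*

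**What the plan says.** Three parts of the SAP define the mediation test.

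- **Path b (Aim 3b).** The b paths "will be the regression coefficients for the mediators when all the mediators are simultaneously added to the GLMM equation predicting PPA used in Aim 1a". The Overview describes that equation as a logistic mixed model in which "the repeated measures will be nested within individuals, which will be nested within their treatment cohort". This sentence is the whole definition of b.
- **Path a (Aim 3a; Power Analysis, Aim 3).** For the power calculation, a "was the slope of change in the mediator over time", assumed large (d > .80). The same section says b "was the relation between the mediator and the outcome over time", without saying whether that relation is within or between people.
- **Test (Aim 3c).** Each arm is tested on its own, and "Significance of mediated pathways will be determined using Bayesian bootstrap mediation analysis".

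The mediators are measured at baseline, weekly in treatment and at each follow-up (protocol sections 3 and 4, Table 2). The only variable the SAP centres is Time. Its example covariates are gender, education and nicotine dependence. A baseline psychological score enters only if the two arms happen to differ on it.

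**The concern.** A random-intercept model treats a person's underlying propensity to abstain as unrelated to the predictors. If people with generally high anxiety sensitivity, withdrawal or negative affect are also people who generally abstain less, that assumption fails. The undivided coefficient then blends two things: what happens to a person's abstinence when that person's mediator changes, and how chronically high scorers differ from chronically low scorers. Only the first is a mechanism of treatment.

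Nothing else in the plan guards against this. Mediation is tested arm by arm and a is a time slope, so randomisation protects neither path. Covariate adjustment triggered by imbalance between arms does not address differences between people within an arm. Because a is expected to be large, the test of the product a x b is in practice a test of b.

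At stake is the third aim, the mechanism. The protocol intends the results to inform a larger follow-up trial, and a mechanism wrongly credited here could be carried into its design.

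**Working it through.** **Inputs from the documents.** Total sample 80, so 40 per arm if allocation is equal (assumed). On average 5 post-quit assessments, 71% of 7 (5/7 = .714). PPA at last follow-up 27% and 43%. Path a of d = .8.

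**Inputs assumed, because the documents give none.** Two-sided alpha 5%; share of mediator variance that is stable .5 to .7; random-intercept SD for abstinence 1.5 to 2.5; correlation of the stable mediator level with abstinence propensity 0, .3 or .5 in size (negative in sign).

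**Step 1: the plan's own figure.** The stated mediation power of at least .81 cannot be reproduced exactly, because alpha, mediator stability and the metric of a medium b are not given. With the undivided coefficient, stable share .5, intercept SD 1.5 and no person-level correlation, simulated power per arm is .55-.56 at b = 0.5 log-odds per SD, .84 at 0.7 and .97 at 0.907 (d = .5, since .5 x π/√3 = .907). So .81 corresponds to a b just under 0.7 and is attainable.

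**Step 2: why the coefficient moves when the true within-person effect is zero.** Take a mediator with SD 1 at a visit, stable share .5, intercept SD 1.5, correlation -.3 and 5 visits.

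- Variance of the person mean: .5 + .5/5 = .60.
- Covariance with abstinence propensity: -.3 x 1.5 x √.5 = -.318.
- Between-person slope: -.318/.60 = -.53.
- Simulated median of the undivided coefficient: -.17 to -.18, about a third of that slope (.18/.53 = .34), although change in the mediator does nothing.

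**Step 3: false mediated pathways.** There were 500 simulated trials per scenario, with one mediator in one arm of 40. The model was a random-intercept logistic model with time and time squared. A 95% Monte Carlo interval for a x b stood in for the Bayesian bootstrap. The true within-person b is 0. Ranges run over both intercept SDs and both PPA rates.

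| Correlation (size) | Undivided b, stable share .5 | Undivided b, stable share .7 | Person mean and deviation split |
|---|---|---|---|
| 0 | 3.6-5.2% | 2.6-6.2% | 3.6-4.6% |
| .3 | 11.6-14.0% | 17.4-20.0% | 3.6-6.4% |
| .5 | 24.0-30.0% | 40.8-47.0% | 2.8-5.8% |

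Simulation error near 5% is about one point: √(.05 x .95/500) = .0097.

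**Step 4: variations, from separate simulations with intercept SD 1.5.**

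- *Mediator lagged one visit:* 17% (.3) and 35% (.5), so the problem is not one of timing.
- *Five mediators entered together, intercorrelated .5, one carrying the link:* 13% and 26% per arm, against 3-5% when split.
- *Five mediators, link spread evenly at .5:* 7-13% per path. The chance of at least one false path is .37-.46, against .20-.24 when split, so about half of that figure is multiplicity.

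**Step 5: which adjustment.** Splitting each post-quit value into the person's own mean and a deviation controls the error but can remove real mediation. Table 1 starts interoceptive exposure in week 1, gives DCS or placebo at sessions 3 to 5, and sets quit day at the start of week 5. A participant who improves before quitting and stays improved has post-quit deviations near zero. True mediation was simulated through pre-quit change that varies between people (SD .6-.8, b of -1 to -1.5, post-quit deviations pure noise). Detection was 3-5% with the split, 16-56% with the undivided coefficient and 21-63% with the undivided coefficient plus the baseline mediator. Under the null of Step 3, the baseline-adjusted version gave about 7% (.3) and 10% (.5).

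**The case against.** The strongest objections are these.

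- **The SAP never says that the mediators are uncentred.** This is inferred from silence, and the SAP refers to a Figure 1 and to a section 3C.2a that are not in the supplied text. That stands as a caution. Even so, a plan that leaves the level of b open has not prespecified it.
- **The inflation is conditional.** It needs a person-level correlation that the documents do not report, and it vanishes at zero. That stands. The largest rates also come from one mediator, whereas Aim 3b enters all of them together.
- **Aim 3 only explores mechanisms.** The SAP's primary goal is feasibility and whether a Stage II study is warranted. That limits the weight of the point but does not answer it.
- **Centring on post-quit means would define away change made before quit day.** This stands in full and determines the form of the fix.

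A reader might infer three stronger things that the documents do not support. First, that the power section defines b as within-person and so contradicts Aim 3b: its wording names no level, and the SAP states no mediation null. Second, that every mediator is a stable trait: the protocol's risk section describes withdrawal symptoms as mostly gone within one to two weeks, and the argument needs only some stable variance. Third, that the cessation comparison is compromised: Aims 1 and 2 do not use path b.

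**Conclusion.** The concern holds in conditional form. As written, Aim 3b does not isolate the effect of change in a mediator, and Aim 3c can label a stable difference between people as a mediated pathway. How often depends on the assumed correlation, stable-variance share and intercept SD. The single-mediator range in Step 3 is an upper guide, and the evenly spread five-mediator rate is a more modest one. The simulations omit the cohort level and replace the Bayesian bootstrap with a Monte Carlo interval. They show that the test can mislead, not that a finding from this trial would be false. The point is worth settling before the mediation models are run, and it is confined to the exploratory aim.

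**What to change.** **Change to Aim 3b.** Enter each participant's baseline (pre-treatment) value of every mediator, together with the visit value or its change from baseline. The two forms give the same b, because b1·M(t) + b2·M(0) = b1·[M(t) - M(0)] + (b1 + b2)·M(0). Define path b as b1, the coefficient of change from baseline, and use only b1 in Aim 3c. Do not report the baseline coefficient as mediation. Change achieved before quit day then still counts.

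**Sensitivity analysis.** Report the split into person mean and within-person deviation over post-quit visits. State that it is stricter and does not see change completed before quit day.

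**Cost.** No new data are needed: Table 2 already schedules all five mediators at baseline. The price is a few sentences and up to five more covariates in arm-wise models of about 40 people. Some inflation remains, because one baseline score measures the stable level with error. The stricter split loses power even when mediation runs through post-quit change: from .84 to .69 at b = -0.7 with one mediator, and from .47 to .29 per arm at b = -0.6 with five. The stated .81 should be recomputed for the revised model, with alpha, mediator stability and the metric of b written down. None of this resolves reverse causation within a visit, where smoking itself may alter withdrawal or affect, and the report should say so.

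### Aim 3c tests mediated pathways only within each arm, so a significant DCS-arm pathway cannot by itself show a DCS mechanism, and the supplied text states no between-arm test or rule that would.

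*SAP*

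**What the plan says.** Protocol section 3 (Purpose) sets Aim 3 as exploring the mechanisms by which PSRT+DCS improves cessation, in a trial whose comparator is PSRT+PBO.

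The SAP (Tests of specific aims) builds the mediation analysis in parts:

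- **Aim 2a** compares the arms on each mediator: "The same analyses in Aim 1a will be used in MLMs to test for treatment differences in the psychological outcomes".
- **Aim 3a** says the a paths "will be calculated as in Aim 2a". Because moderation is expected, it then adds that "separate analyses will be conducted to calculate the" a paths for each condition. The c "path will be calculated as in Aim 1a".
- **Aim 3b** takes the b paths as the mediator coefficients "when all the mediators are simultaneously added to the GLMM equation predicting PPA used in Aim 1a". That model contains both arms.
- **Aim 3c** gives the significance test: "Tests of the mediated pathways will be conducted separately for each treatment condition", citing moderated mediation as the reason, with a Bayesian bootstrap.

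The SAP Power Analysis for Aim 3 first gives power above .95 to detect moderation of path a at d = .50. It continues: "Next we calculated the power to detect longitudinal mediation for each treatment group, over time". Here path a "was the slope of change in the mediator over time", assumed large (d > .80), with a medium b. The result is power of at least .81.

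**The concern.** Within an arm, path a is change from before to after treatment. It is not a randomised effect. PSRT, the patch and the passage of time can all produce it, and they are present in both arms. Protocol section 3 reports that PSRT without DCS already lowered anxiety sensitivity, a listed mediator, more than standard cessation treatment did. The SAP's power calculation itself assumes a large a path for each group, placebo included. A significant a × b in the DCS arm is therefore what the plan expects whether or not DCS does anything.

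The inference about DCS has to come from the difference between arms. The components for that are planned, but Aim 3c does not combine them, and nothing says a DCS mechanism may be claimed only if they agree. At stake is the interpretation of Aim 3. Protocol section 3 expects the trial to isolate explanatory mechanisms and to inform a larger follow-up trial, so a PSRT pathway credited to DCS would carry forward.

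**Working it through.** **Inputs.** N = 80, a-path d > .80, medium b, within-group power at least .81, and a-path moderation power over .95 at d = .50 (all SAP, Power Analysis). My assumptions, because the documents do not state them: 40 per arm, two-sided 5%, one mediator, one change score per person, d in SD units of individual change.

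**1. The plan's .81.** I simulated one arm of 40 with a mean mediator change of .80 SD and a 95% Monte Carlo interval for a × b (4,000 trials). Power was .51, .64, .73, .80 and .86 for standardised b of .30, .35, .39, .42 and .45. The stated .81 lies in this range but cannot be confirmed: the value of b, the number of assessments and the within-person correlation are not given.

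**2. The plan's .95.** For d = .50 with one score per person, z = .50/√(2/40) = 2.24 and power = Φ(2.24 − 1.96) ≈ .61. Averaging five measures gives .96 at correlation .2 and .82 at .5. The .95 thus depends on inputs not shown, and I carry both .61 and .95 below.

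**3. What Aim 3c and the alternatives do.** Two arms of 40, b = .42 in both, 4,000 trials. The within-arm tests use each arm's own b, and the shared-b contrast pools b over arms:

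| True a (DCS, PBO) | DCS arm significant | PBO arm significant | DCS only | (a_DCS − a_PBO) × shared b | Difference in a × b, per-arm b |
|---|---|---|---|---|---|
| .80, .80 (DCS inert) | 80.2% | 80.2% | 16.1% | 4.7% | 5.1% |
| 1.30, .80 | 79.7% | 80.7% | 15.2% | 58.6% | 13.2% |
| .80, .30 | 80.6% | 35.3% | 51.7% | 58.5% | 26.2% |

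The DCS-arm result is about 80% whether DCS is inert or shifts the mediator by d = .50. Taking .81 per arm as independent, the DCS-only pattern with DCS inert is .81 × .19 = .15, in line with the table.

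**4. Closed-form check of the joint rule** (Aim 2a difference and Aim 3b b path both significant). Path a within an arm: z = .80 × √40 = 5.06, power Φ(3.10) = .999. Set b at z = 2.83, so that its power is Φ(.87) = .81 and within-arm power is .999 × .81 ≈ .81. If b is pooled over arms, z = 2.83 × √2 = 4.00 and its power is Φ(2.04) = .98.

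- DCS inert: .05 × .81 = .04; with pooled b, .05 × .98 = .049.
- a-difference d = .50: .61 × .81 = .49; with pooled b, .61 × .98 = .60.
- a-difference power .95: .95 × .81 = .77; with pooled b, .95 × .98 = .93.

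If the pooled b also entered the per-arm pathway, that pathway would be significant in about .98 of trials. The 80% therefore belongs with b no more precise than one arm provides.

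**5. Logistic outcome.** 40 per arm, about 35% abstinent, log-odds .72 per SD of the mediator, 6,000 trials. DCS inert: DCS arm 79.9%, placebo arm 79.8%, shared-b contrast 3.3%, joint rule 4.0%. At an a-difference of d = .50: contrast .46, joint rule .49.

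**The case against.** The strongest reply is that the plan is a moderated-mediation analysis and already compares the arms. Aim 3a expects the a paths to differ, Aim 2a tests that difference, and the power section takes a-path moderation as its first step and within-group mediation as the next. A natural reading is moderation first, then per-arm effects. This stands in large part: a reader might infer that the plan has no between-arm comparison of the mediators, and that would be wrong. But the ordering is stated only for the power calculation. It is not a rule for drawing conclusions, and Aim 3c does not refer to it.

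A reader might also infer that the SAP intends to credit a DCS-arm pathway to DCS. No passage says so. A significant within-arm pathway is a valid result, and it bears on the protocol's broader interest in panic–smoking mechanisms. Nor is the 80% a false-positive rate: in that scenario the within-arm pathway truly exists.

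Figure 1, section 3C.2a and the cited moderated-mediation source are not in the supplied documents and might contain the joining step. The point rests on the SAP text alone.

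Finally, Aim 3 is exploratory, in a Stage IB trial whose main goals are feasibility and whether a Stage II study is warranted. That limits the severity but does not supply the missing rule.

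**Conclusion.** The point holds as a gap in inference. Aim 3c as written cannot separate a DCS mechanism from PSRT and patch effects: its DCS-arm result is significant in about 80% of trials whether DCS is inert or moves the mediator by d = .50. A between-arm indirect effect, or the joint rule, is significant in about 3% to 5% when DCS is inert.

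Comparing significance across arms does not repair this if b is estimated per arm, since the DCS-only pattern then arises in about 15% of trials with DCS inert. With a shared b it is rare (about 1% to 3% in a normal-approximation run), but the SAP leaves open which applies: Aim 3b takes b from the model with both arms, while Aim 3c and its power calculation work by arm.

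The sizes rest on the assumptions listed in the working, and the plan's .81 and .95 could not be confirmed. The primary outcomes are unaffected. I rate this a minor to moderate change.

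**What to change.** In Aim 3c, state that the test of a DCS mechanism is (a_DCS − a_PBO) × b with one bootstrap interval, using the shared b from the Aim 1a GLMM that Aim 3b describes. Equivalently for practical purposes, add one sentence that a DCS mechanism is claimed for a mediator only if both its Aim 2a treatment difference and its Aim 3b b path are significant. State explicitly that b is shared, and report per-arm a × b as descriptive. In the Power Analysis, say that the .81 is power within a treatment group, not for this contrast, and add the contrast's power.

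The cost is SAP wording plus one contrast from models already planned, with no new data. The downside is limited power: at an a-path difference of d = .50, about .45 to .60 with shared b. It would be higher, about .75 to .93, if the SAP's .95 for a-path moderation is accepted. If the sponsor prefers per-arm b, the contrast becomes the difference in a × b, with power of only about .13 to .26 at d = .50. A null result would therefore say little, and the SAP should say so in advance.

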3. PURPOSE

Approximately 9-15 million smokers in the U.S. meet criteria for at least one anxiety disorder during their lifetime (Kessler et al., 2005), and these individuals experience significant challenges quitting tobacco (Piper et al., 2010; [name] et al., 2008). Yet, little attention has been given to the maintenance of tobacco use among persons with anxiety disorders, and in particular, smokers with a history of panic attacks. This group is especially important to study because research shows that they have significantly lower quit rates than smokers with no history of panic attacks, and that they respond the same to placebo, single cessation pharmacotherapy, and combination cessation pharmacotherapy (Piper et al., 2010a). Recent efforts from our group have led to the development of a cognitive-behavioral program, Panic and Smoking Reduction Treatment (PSRT), which integrates interoceptive exposure, cognitive restructuring, and psychoeducation exercises with standard smoking cessation strategies and nicotine replacement therapy. Early testing of this program indicates that this targeted smoking cessation treatment for smokers with panic attacks is efficacious, but leaves room for improvement. Specifically, a study examining the efficacy of PSRT revealed that individuals receiving PSRT evidenced significantly greater reductions in anxiety sensitivity and were more likely to be smoke free than those receiving standard smoking cessation treatment ([name] et al., 2008). However, only 42.7% of the PSRT condition were smoke-free at 16 weeks post-quit.

The current study seeks to evaluate whether d-cycloserine (DCS) can augment the efficacy of PSRT. DCS is a partial NMDA agonist, which has shown to enhance the retention of fear extinction (Davis et al., 2005; Richardson et al., 2004; Ledgerwood et al., 2004; Ledgerwood et al., 2005), which is a key mechanism underlying the efficacy of PSRT ([name] et al., 2008). Of note, DCS has shown to be an effective and safe augmentative strategy in panic disorder ([name] et al., 2010), which may make it a particularly effective strategy for smokers with panic attacks.

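### Does the 27% control rate in the Aim 1a power analysis conflict with the protocol's 42.7% result for PSRT?

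*SAP*

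**What the plan says.** The SAP's Power Analysis sets out to give the effect sizes that 80 participants can detect with 80% power. For Aim 1a it lists two assumptions: an average of five assessments per participant, and "a 27% PPA in PSRT+PBO at the last follow-up", the latter from a cited publication. Many PSRT+DCS rates were tried against that single control rate. The result is .80 power if "the PPA rate in PSRT+DCS at the follow-up was 43% or greater". The SAP converts 43% versus 27% to a Cohen's effect size of .17 and concludes: "Thus, we have sufficient power to detect a smaller than medium effect". The same pair of rates is used again in the Aim 3 mediation simulation.

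The protocol's Purpose section describes PSRT as combining panic-focused work "with standard smoking cessation strategies and nicotine replacement therapy". It reports that earlier PSRT patients "were more likely to be smoke free than those receiving standard smoking cessation treatment", but that "only 42.7% of the PSRT condition were smoke-free at 16 weeks post-quit". It also says of smokers with a history of panic attacks that "they respond the same to placebo, single cessation pharmacotherapy, and combination cessation pharmacotherapy". That statement carries nearly the same citation label as the 27%.

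**The concern.** The control arm is PSRT with nicotine patch and placebo, and the earlier PSRT programme also included nicotine replacement. On its face, the best guide to the control rate is the 42.7% in the protocol, yet the power analysis uses 27% without comment. The source label attached to 27% appears in the protocol only for work that is not described as PSRT. If 27% came from ordinary cessation treatment, the protocol's own statement that PSRT did better would point to a higher control rate.

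The difference in time point does not obviously close the gap. The SAP says "PPA is expected to decrease rapidly at first and then level off over time", whereas going from 42.7% at week 16 to 27% at week 24 would be a late fall of 15.7 points.

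At stake would be the headline planning figure. A 43% abstinence rate with DCS would be no better than the rate already reported for PSRT alone. A reader could conclude that the trial's sensitivity is overstated, and that the mediation power of .81, which uses the same two rates, is affected too.

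**Working it through.** **Inputs.** From the SAP: 80 participants, five assessments each on average, 27% versus 43%, power .80, effect size .17. From the protocol: 42.7% at week 16. Not stated, so assumed here: 40 per arm, two-sided alpha .05, and a difference between arms that is constant over visits.

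**Step 1: the SAP's effect size.** With p0 = .27 and p1 = .43, the mean rate is .35.

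w = (p1 − p0) / (2·√[.35 × .65]) = .16 / .954 = .168, which matches the stated .17.

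The odds ratio is (.43/.57)/(.27/.73) = 2.04.

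**Step 2: calibrate to the SAP's .80.** The simulation cannot be rerun, because its alpha, within-person correlation, time curve and cohort variance are not given. Its .80 is therefore taken as correct, and the effective number per arm that yields it is found from

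power = Φ{ (|p1 − p0| − 1.96·√[2·p̄(1 − p̄)/n]) / √[(p0(1 − p0) + p1(1 − p1))/n] }.

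At n = 138.3 this is (.16 − 1.96 × .0574)/.0565 = .84, and Φ(.84) = .80. Five visits from 40 people are 200 observations, so the design effect is 200/138.3 = 1.446. The implied within-person correlation is (1.446 − 1)/4 = .11.

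**Step 3: hold n at 138.3 and vary the control rate.**

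| Control rate | Detectable DCS rate | Difference (points) | w | Odds ratio | Power if DCS is 43% | Power if odds ratio is 2.04 |
|---|---|---|---|---|---|---|
| 27% | 43.0% | 16.0 | .168 | 2.04 | .80 | .80 |
| 30% | 46.3% | 16.3 | .168 | 2.01 | .61 | .82 |
| 35% | 51.6% | 16.6 | .168 | 1.98 | .28 | .83 |
| 40% | 56.8% | 16.8 | .168 | 1.97 | .07 | .84 |
| 42.7% | 59.5% | 16.8 | .168 | 1.97 | .03 | .84 |

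Calibrating to a one-sided .05 test instead gives the same detectable rates. At a 42.7% control rate, power for a gain of exactly 16 points is .76, against .80 at 27%.

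**Step 4: read the table.** The absolute DCS rate rises almost one for one with the control rate. The effect that can be detected hardly changes, whether measured as a difference, as w or as an odds ratio. The column that fixes DCS at 43% falls steeply only because the treatment effect shrinks towards zero as the control rate approaches 43%. It says nothing about lost sensitivity. On the odds-ratio scale, which is the scale of the planned logistic model, 27% is slightly the harder case.

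**Step 5: drop the calibration.** With other within-person correlations the level shifts, but the comparison does not. At correlation .5 the detectable rates are 50.4% (control 27%) and 66.6% (control 42.7%), differences of 23.4 and 23.9 points. At .8 they are 54.9% and 70.8%, differences of 27.9 and 28.1 points. Whether .80 is attainable at 27% versus 43% is a separate question from the choice of control rate.

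**The case for a change.** The strongest case for a change is that the simulation's stated product is a minimum detectable abstinence rate, that this rate rests on one unexplained input, and that a three-point rise in the control rate takes power at 43% from .80 to .61. The trial is meant to inform a larger study, so its planners should not carry 43% away as a fixed benchmark. A short range of control rates would cost almost nothing.

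Part of this stands. The SAP gives no reason for preferring 27% to the protocol's figure and shows no other control rate.

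The rest does not carry. The condition is not hidden: 27% is listed as an assumption just before the 43% and repeated beside it when the effect size is computed. Neither document uses 43% as a threshold for proceeding. The 42.7% is not the same quantity either. It is a smoke-free rate at week 16 in an earlier study, whose abstinence definition and handling of dropouts the documents do not give, whereas the SAP needs 7-day point prevalence at week 24. The similarly labelled source in the protocol concerns smokers with a history of panic attacks, the population enrolled here. If it is the same paper, that is a plausible reason for choosing it. Joining the two figures into one declining curve treats two studies as a single cohort.

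**Conclusion.** This is a gap in justification, and no stated figure is shown to be wrong. If the control rate were as high as 42.7%, the detectable DCS rate would be roughly 60% instead of 43%. The detectable difference would stay at about 16 to 17 points and w at .17, so the SAP's conclusion about a smaller than medium effect is unaffected. The sample size is fixed at 80, the SAP already disclaims power for small differences and describes a Stage IB study, and the models, tests and decisions do not depend on the control rate assumed for planning. With the SAP last updated in June 2017 and data collection expected to end that August, a rerun would alter nothing that is done. For the mediation power of .81, the documents do not show even the direction of any change.

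The figures rest on equal arms, alpha .05, the SAP's .80 taken as given and a constant difference across visits. The slope test and the nesting within cohorts were not modelled, so the rates are approximate. The finding that the detectable difference barely depends on the control rate also holds at the higher within-person correlations tried. A sentence explaining 27% would help a reader, but the plan does not need to change.
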